7.2 Sample

The total population will be 166 cases, which will be randomly included and distributed in 2 study groups. Both with diagnosis of grade I to III Pterygium.

Subjects with bilateral Pterygium, in which both eyes meet the selection criteria, can participate with both eyes, taking each eye as one case.

Group 1 will receive Zebesten® ophthalmic solution together with Na hyaluronate.

Group 2 will receive placebo (formulation with no drug substance) together with Na hyaluronate.

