12.4 SAMPLE SIZE CALCULATION

Sample size protocol SOPH155-0415/IV

According to the objectives of the study to evaluate the Zebesten ® effect in subjects with primary pterygium, the variables of primary outcome stipulated in the design were:

- Conjunctival hyperemia
- TRL

Both variables are considered, using similar literature, to perform the calculation of the sample size to meet with the study objectives.

Conjunctival hyperemia

The sample size was calculated according to the formula for the continuous quantitative variables:

$$n = 2 \frac{(Z_{\alpha/2} - Z_{\beta})(\delta)}{d^2}$$

With a statistical trust of 95% that corresponds to the type I error, and is the same as 1.96, with a potency of 80% that corresponds to the type II error, and equals to 0.84. It is considered as a standard deviation for the increase of 0.4 degrees of severity1 in the scale of conjunctival hyperemia after a pterygium surgery, with an expected difference of at least 2.9 degrees of severity.

Based on the previous the result was 69 cases (eyes) per group, which was incremented 20% by consideration of the losses (14 subjects), with **a total of 83 cases per group**, with a total population of study of **166 eyes to treat**.⁸

Tear film breakup time

The sample size was calculated according to the formula for continuous quantitative variables:

$$n = 2 \frac{(Z \propto -Z_1 - \beta)(\delta)}{d^2}$$

With a statistical trust of 95% that corresponds to the type I error, and is the same as 1.96, with a potency of 80% that corresponds to the type II error, and equals to 0.84. It's considered as a standard deviation for the increase of 1.47 seconds 2 in the tear film breakup time posterior to 60 days of ciclosporin application A, with an expected difference of at least 10.2 seconds.

Based on the previous the result was of 120 cases per group, which was incremented 20% per consideration to the losses (24 cases), with a total of **144 cases per group**, with a total population of study of **288 eyes to treat**.

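### Section 12.4 derives 166 and 288 eyes for two primary outcomes, section 7.2 enrols 166 without explanation, and neither base figure follows from its inputs

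*Combined protocol and SAP*

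**What the plan says.** Section 12.4 names conjunctival hyperemia and tear film breakup time as primary outcomes and says: "Both variables are considered, using similar literature, to perform the calculation of the sample size to meet with the study objectives". Both calculations use 1.96 for 95% confidence and 0.84 for 80% power.

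- **Hyperemia.** The inputs are "It is considered as a standard deviation for the increase of 0.4 degrees of severity1 in the scale of conjunctival hyperemia" after pterygium surgery, "with an expected difference of at least 2.9 degrees of severity". The result: "Based on the previous the result was 69 cases (eyes) per group, which was incremented 20% by consideration of the losses (14 subjects". That makes 83 per group and 166 eyes.
- **Breakup time.** The inputs are a "standard deviation for the increase of 1.47 seconds 2 in the tear film breakup time posterior to 60 days of ciclosporin application", "with an expected difference of at least 10.2 seconds". The result: "Based on the previous the result was of 120 cases per group, which was incremented 20% per consideration to the losses (24 cases". That makes 144 per group and 288 eyes.

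Section 7.2 then sets the enrolment: "The total population will be 166 cases, which will be randomly included and distributed in 2 study groups". It also lets a subject with bilateral disease contribute each eye as a separate case.

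Sections 6 and 13 list hyperemia, breakup time and adverse events as primary. Section 5.1.2 and section 13.2 place breakup time under safety, and section 13.3 leaves it out of efficacy. The table in 13.3 classes hyperemia as ordinal with four levels. Section 14 gives a single significance level of 0.05 and no rule for more than one primary outcome.

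**The concern.** If both outcomes determine the size, the larger requirement should govern, or the plan should say why it does not. It does neither: 166 is 58% of 288.

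The inputs are a second problem. In each calculation the printed difference is about seven times the printed SD, so a handful of eyes would suffice, yet the plan reports 69 and 120 per group. For hyperemia, a 2.9-grade difference between groups is almost the whole three-step span of the listed scale (four steps if a normal grade is also recorded).

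At stake is whether anyone can judge if 166 eyes are too few, enough or too many. The unclear role of breakup time adds to this: the plan does not say whether that outcome needs to be powered, or whether a positive result on it alone would count as success.

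**Working it through.** **Inputs** (all section 12.4): z values 1.96 and 0.84, sum 2.80; hyperemia SD 0.4, difference 2.9; breakup time SD 1.47 s, difference 10.2 s. Allocation is 1:1 (section 7.5). Eyes are treated as independent throughout.

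**Loss step.** 69 × 1.20 = 82.8, i.e. 83, and 120 × 1.20 = 144, so the totals 166 and 288 follow from the base figures. Multiplying by 1.20 does not preserve the base after a 20% loss: 83 × 0.8 = 66.4. Division would give 69/0.8 = 86.25, i.e. 87, and 120/0.8 = 150.

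**Base figures.** Standard formula: n per group = 2 × (1.96 + 0.84)² × SD² / d².

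| Outcome | Inputs as printed | SD and d exchanged | Plan |
|---|---|---|---|
| Hyperemia | 2 × 7.84 × 0.4² / 2.9² = 0.30, i.e. 1 | 2 × 7.84 × 2.9² / 0.4² = 824 | 69 |
| Breakup time | 2 × 7.84 × 1.47² / 10.2² = 0.33, i.e. 1 | 2 × 7.84 × 10.2² / 1.47² = 755 | 120 |

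Both orders are shown because the translated phrase introducing the SD is ambiguous.

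**The formula as it appears in the text** has a minus sign and no squares in the numerator. Taken literally, 2 × 1.12 × SD / d² gives 0.11 for hyperemia and 0.03 for breakup time (exchanged: 40.6 and 10.6). With a plus sign it gives 0.27 and 0.08 (exchanged: 101.5 and 26.4). None is 69 or 120. The lost squares may come from reading the PDF.

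**A near match for 120.** Subtracting the z values, squaring, and exchanging SD and difference gives 2 × (1.12 × 10.2 / 1.47)² = 120.8. This is not a valid calculation. The same steps for hyperemia give 2 × (1.12 × 2.9 / 0.4)² = 131.9, not 69.

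**Power at the enrolled size.** Power = Φ((d/SD) × √(n/2) − 1.96). The face-value rows back-solve d/SD from the plan's own claim of 80%: 2.8/√34.5 = 0.4767 for 69, and 2.8/√60 = 0.3615 for 120.

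| Reading | d/SD | n = 66 | n = 69 | n = 83 |
|---|---|---|---|---|
| Hyperemia, as printed | 7.25 | >99.9% | >99.9% | >99.9% |
| Hyperemia, exchanged | 0.1379 | 12.1% | 12.5% | 14.2% |
| Hyperemia, 69 at face value | 0.4767 | 78.2% | 80.0% | 86.7% |
| Breakup time, as printed | 6.94 | >99.9% | >99.9% | >99.9% |
| Breakup time, exchanged | 0.1441 | 12.9% | 13.3% | 15.1% |
| Breakup time, 120 at face value | 0.3615 | 54.6% | 56.5% | 64.4% |

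**What the enrolled size can detect.** For any continuous outcome, the difference detectable with 80% power is 2.8/√(n/2) SD: 0.49 SD at 66 per group, 0.48 at 69 and 0.43 at 83.

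**False-positive risk.** If hyperemia and breakup time were each tested at 0.05 and either could establish success, the chance of at least one false positive is 1 − 0.95² = 9.75% if independent, and at most 10%.

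**The case against.** - **166 may be deliberate.** The study design statement and specific purpose 1 concern hyperemia, section 13.3 lists it under efficacy, and section 13.2 puts breakup time under safety. Sizing on hyperemia would fit. But no section says so, section 12.4 says both outcomes are used, and the hyperemia calculation does not reproduce either.
- **120 has a likely origin.** The 120.8 match suggests that 10.2 was used as the SD for breakup time, so the two readings may not be equally likely. This stands as a clue. It supports the exchanged reading, under which power is low, and it rests on an invalid formula that fails for hyperemia.
- **Sizing a graded scale by means is common.** True, and not an error in itself. The difficulty is a printed difference that nearly spans the listed scale.
- **Other success rules are possible.** If both outcomes had to be positive, alpha would not be inflated and the question would be joint power. If adverse events, also listed as primary, could count too, the figure would be 1 − 0.95³ = 14.3% if independent and at most 15%. Both points are fair. They show that the plan leaves the rule open.
- **Removing 288 may be premature.** A sound recalculation could land near that number. It could, but the present 288 is not evidence for it.

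**Conclusion.** The concern holds. Section 12.4 gives two totals for two outcomes it calls primary, and section 7.2 adopts the smaller without a reason. Neither 69 nor 120 per group follows from its stated inputs by any valid formula tried.

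The ratio of 166 to 288 is an unexplained inconsistency, not a demonstrated shortfall. At 69 to 83 per group, power for either outcome is about 100% on the inputs as printed and about 13% to 15% with them exchanged. Taking the plan's 120 at face value, breakup time has 55% to 64% power at 66 to 83 per group. None of these is an estimate of the trial's true power; together they show that the 80% claim has no support.

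The figures assume independent eyes, equal groups and the normal approximation. Counting both eyes of a subject as separate cases would change them by an amount the documents do not let us calculate. The multiplicity point applies only if more than one outcome can establish success; if breakup time is safety only, it does not arise for that outcome. This must be fixed, because the size of the trial currently has no reproducible basis.

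**What to change.** 1. Redo both calculations. State which value is the SD and which the between-group difference, give a source for each, and print the correct formula.
2. For hyperemia, use a method suited to an ordinal grade and matched to the test that section 14 will apply. Allow for subjects who contribute both eyes, and for losses by division.
3. State the power that 166 eyes deliver for each outcome, or the difference detectable with 80% power. Withdraw the 288-eye, 80% power statement. Do not adopt 288, or any power figure above, as a target.
4. Settle the role of breakup time. Either move it to the safety set, where 13.2 already lists it, and report the difference with a 95% confidence interval; or keep it primary and test it after hyperemia in a fixed sequence at 0.05, with its restated power. If the sponsor intends both outcomes to be required, say so and give the joint power. State also whether adverse events are tested or only described.

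The cost is protocol and SAP wording plus one recalculation per outcome. Breakup time may lose its confirmatory claim, and the restated power may be less favourable. More eyes would be needed only if the sponsor then wants 80% power for a sourced difference that 166 eyes cannot detect.

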13. STUDY VARIABLES

Independent variables

- Pharmacological intervention
 - Zebesten® + Sodium hyaluronate 4 mg/ml
 - Placebo (vehicle + Sodium hyaluronate 4 mg/ml)

Dependent variable

- Primary outcome variable
 - Conjunctival hyperemia
 - Tear film breakup time
 - Adverse events

- **Secondary outcome variable**

- burning
- Foreign body sensation
- Photophobia
- Questionnaire score OSDI
- Fluorescein stain
- Visual capacity
- Intraocular pressure

Intervening variables

- Work activity with sun exposure without ocular protection.
- Areas with air conditioner.
- Use of ocular devices that modify the lubrication.

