10. DESCRIPTION OF THE PROCEDURES

10.1 General and Ophthalmic Medical Record

It refers to a systems review highlighting the medical and surgical history, indicating the start, evolution and, if applicable, the end of previous conditions.

List the drug products taken and the dates of the last dose; specify their administration route.

A general clinical examination will be performed, including vital signs (blood pressure, body temperature, breaths per minute and heart rate) and anthropometric parameters (weight, size, complexion).

Patients will be asked about previous, chronic or acute ocular conditions, specifying onset or diagnosis time, and their evolution.

If applicable, the optical correction devices used by the subject will be listed, such as frame glasses, contact lenses, magnifying glass, etc. Similarly, the evolution time and use period will be stated.

Then, topical drug products used in eyes and eye adnexa will be investigated. In the case of any systemic drug product directly related to a condition of the eyes or eye adnexa (eyelids, eye socket, lacrimal duct, glands, etc.), it must also be recorded in this section.

Any finding that prevents the protocol procedures from being carried out or the subject from remaining in the study must be recorded. Yes/ No must be indicated in the FRC. In the case of any finding, it must be specified.

It must also be recorded if the subject performs outdoor activities for more than 8 hours (Yes/ No) and if they perform activities in a place with air conditioning for more than 8 hours a day (Yes/ No).

The grade of pterygium must be recorded according to the above classification.

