14. PROPOSED STATISTICAL ANALYSIS

The statistical analysis will be performed by a researcher blinded to the intervention groups.

The continuous quantitative variables will be expressed and presented via measures of central tendencies and of dispersion (media, standard deviation and ranges).

The nominal qualitative variables and ordinals will be presented via frequencies and proportions.

The Kolmogorov-Smirnov test will be performed in order to know the normal distribution or not of the obtained results in each study group. Also, the Levene test will be performed in order to know if the variables are the same or different.

Assuming a normal distribution of the data, the intra-group differences will be determined via the t test for paired samples, in the case of the quantitative variables. For the quantitative variables the χ^2 test (chi squared) will be used and in case that the expected frequencies are less than 5 the exact Fisher test will be used.

The differences among the groups will be analyzed via the t test in case of quantitative variables. For the quantitative variables tables of contingency 2x2 will be made and the differences will be calculated via χ^2 (chi squared) with Yates correction in case that the expected frequencies are less than 5 the exact Fisher test will be used).

The level of significance will be alpha of 0.05 or less.

A final statistical analysis will be included to all the subjects that complete 3 visits in the chronogram of activities.

15. Results report

The results obtained during the development of the investigation's protocol will be the responsibility of the sponsor, who is under obligation of reporting them to the pertinent authorities. Plus each one of the participating researchers will receive a results report.

The objective is to achieve the publication of the study on an international magazine with the objective of disseminate the scientific knowledge obtained.

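### Section 13 names three intervening variables and section 10.1 records related baseline items and pterygium grade, but section 14 gives none of them a role in comparing the arms; the cost is some precision and prespecified protection against chance imbalance, not validity.

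*Combined protocol and SAP*

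**What the plan says.** Section 13 (Study variables) sets three intervening variables beside the independent and dependent ones: "Work activity with sun exposure without ocular protection", "Areas with air conditioner" and "Use of ocular devices that modify the lubrication". It does not define the term or say what the variables are for. The measurement table in section 13.3 has a row for pterygium grade but none for these three.

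Section 10.1 (General and Ophthalmic Medical Record) collects related items at baseline:
- outdoor exposure: "It must also be recorded if the subject performs outdoor activities for more than 8 hours (Yes/ No");
- air conditioning: "if they perform activities in a place with air conditioning for more than 8 hours a day (Yes/ No");
- devices: "the optical correction devices used by the subject will be listed, such as frame glasses, contact lenses, magnifying glass, etc";
- pterygium: "The grade of pterygium must be recorded according to the above classification".

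Section 14 (Proposed statistical analysis) then states: "The differences among the groups will be analyzed via the t test in case of quantitative variables". The remaining variables go into 2x2 tables with a chi-squared or Fisher test. It names no covariate, regression model, stratified test or subgroup. Section 7.5 specifies simple 1:1 randomisation with no stratification factor, and section 7.2 lets a subject with bilateral disease contribute both eyes as two cases.

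**The concern.** Variables that a protocol singles out as intervening, and takes the trouble to record, would normally have a stated use. Here they are handled neither by stratification nor in the analysis. The entry criteria limit grade to I to III but do not restrict sun exposure, air conditioning or contact lens wear.

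These factors could plausibly affect hyperemia and breakup time, which are both primary, and the OSDI score. The OSDI in Appendix 3 itself asks about discomfort in air-conditioned places. Two things are at stake. Variation that the factors could explain stays in the error term. And if the arms differ on one of them by chance, any adjustment would have to be chosen after the data are seen, which is open to challenge.

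A smaller, separate problem is that the first variable cannot be built as section 13 words it, because section 10.1 asks about outdoor hours and not about ocular protection.

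**Working it through.** **1. What is named, what is recorded, what is analysed**

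| Section 13 | Section 10.1 | Section 14 |
|---|---|---|
| Sun-exposed work, no ocular protection | Outdoor activity over 8 h, yes/no; protection not asked | No role |
| Air-conditioned areas | Air conditioning over 8 h a day, yes/no | No role |
| Devices that modify lubrication | List of optical correction devices, including frame glasses and magnifying glasses as well as contact lenses | No role |
| (not listed as intervening) | Pterygium grade | No role |

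The air-conditioning item matches fairly well. The other two match loosely.

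**2. The plan's own figure.** Section 12.4 gives 69 eyes per group for hyperemia at two-sided 5% and 80% power. With the loss allowance, 69 × 1.2 = 82.8, so 83 per group and 166 in total; that step reproduces. The 69 does not: with SD 0.4 and difference 2.9, 2 × (1.96 + 0.84)² × 0.4² / 2.9² = 0.30, so 1 per group. The 80% below is therefore the plan's nominal figure, not one its inputs support.

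**3. Precision.** In a linear model, adjusting for factors with joint R² multiplies the standard error by √(1 − R²). From a nominal 80%, power = Φ((1.96 + 0.8416)/√(1 − R²) − 1.96). The documents give no R², so it is assumed over a range:

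| R² | Power |
|---|---|
| 0.05 | 82% |
| 0.10 | 84% |
| 0.15 | 86% |

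A gain of 5 points needs R² of about 0.13. The gain is smaller if the model also contains the baseline value of the outcome.

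For breakup time the base is lower, because section 12.4 asks for 120 per group before losses and the trial is sized on 69. The standardised effect back-solved from 120 is 2.8 × √(2/120) = 0.361. At 69 per group that gives Φ(0.361 × √(69/2) − 1.96) = 56%, and R² of 0.05 to 0.15 would raise it to about 59% to 63%.

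**4. Chance imbalance.** For a binary factor of prevalence p with n independent cases per arm, the standard error of the between-arm difference is √(2p(1 − p)/n). With n = 83, and p assumed because the documents give none:

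| p | Standard error | P(difference ≥ 10 points), one factor | At least one of three independent factors |
|---|---|---|---|
| 10% | 0.047 | 3% | 9% |
| 20% | 0.062 | 11% | 29% |
| 30% | 0.071 | 16% | 41% |
| 50% | 0.078 | 20% | 48% |

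The exposures belong to subjects, so if bilateral cases share an arm, fewer independent units raise these figures. At an assumed 50 subjects per arm and p = 50%, they are 32% and 68%.

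**5. What such an imbalance does to the result.** Take p = 50% and a factor explaining 5% of variance. Its effect is √(0.05/0.25) = 0.447 SD, so a 10-point imbalance shifts the arm difference by 0.045 SD. The standard error at 69 per arm is √(2/69) = 0.170 SD, and the effect back-solved from 69 is 2.8 × 0.170 = 0.477 SD. The shift is about a quarter of one standard error and about 9% of that effect.

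**The case against.** The strongest reply is that nothing here is an error. Under 1:1 randomisation the unadjusted comparison is unbiased over repeated allocations, and its type I error already allows for chance imbalance. That stands. A reader might infer that the primary result is confounded by these exposures, or cannot be separated from them. The documents do not support this: allocation is random, and the recorded data would permit a supportive adjusted analysis even as the plan is written. Only the prespecification is missing.

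A reader might also take an imbalance probability of 48% or 68% as the chance of a misleading result. It is not. The 10-point threshold is arbitrary, 50% prevalence is the worst case, and step 5 shows that the resulting shift is small.

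The power figures are open to challenge too, and those limits stand. R² is assumed, the 80% base does not follow from the stated SD and difference (with those inputs power at 69 would be near 100%), and the formula is for a linear model. It says nothing direct about an ordinal model for hyperemia, where covariates change the estimand to a conditional odds ratio.

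Finally, the protocol does not define intervening variables. That the sponsor expects them to act on the outcome is a natural inference, not a statement in the text. Nor is grade wholly unused in the design, since eligibility restricts it. Neither point answers the observation that section 14 leaves the recorded data without a role between the arms.

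**Conclusion.** The point holds as a modest, optional improvement in efficiency and prespecification. The unadjusted analysis remains valid. The likely gain is a few points of power: about 2 to 6 from a nominal 80% if the factors jointly explain 5% to 15% of outcome variance in a linear model, and less once the baseline outcome is also modelled. The true size cannot be computed, because the documents give neither the prevalence of the exposures nor their relation to the outcomes. The mismatch over ocular protection does not depend on any of these assumptions and needs correcting in either case.

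**What to change.** In section 14, prespecify as the primary between-arm analysis a model adjusted for baseline pterygium grade (I, II, III), outdoor activity over 8 h, air conditioning over 8 h and contact lens use. Use a linear model for breakup time and an ordinal model for hyperemia, each accounting for two eyes from the same subject. Report the unadjusted result as supportive.

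State which section 10.1 field represents each section 13 variable, in particular that contact lens use, rather than any optical device, stands for devices that modify lubrication. Align sections 13 and 10.1 on ocular protection, either by rewording section 13 or by adding a yes/no item to the case report form.

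The cost is wording in the analysis section, five degrees of freedom (two for grade, three for the binary items) out of about 138 evaluable cases (2 × 69), fewer in subjects if many are bilateral, and at most one extra item. The hyperemia effect becomes a conditional odds ratio, which should be said when it is reported.
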